#### **2.3.1.2 Primary efficacy Analyses**

For primary efficacy analyses, for each of the main outcome of the study a separate generalized linear mixed model is fitted with the model specification corresponding to the scale level of the outcome under investigation. Thus, for quality of life, caregiver burden and neuropsychiatric symptoms linear mixed regressions will be used assuming a Gaussian distribution, while for antidementive drug treatment and PIM prescription logistic mixed models will be used. To account for the stochastic dependency of patients treated by the same GP, the GP will be included as random effect variable.

The follow up outcome variable at  $T_1$  (twelve months after finishing the baseline) will be the dependent variable in these analyses; the study group is the predictor of interest, while the baseline value ( $T_0$ ) of the outcome variable will be included as covariate to diminish residual variance and to account for inter-individual variance at baseline. Furthermore, sociodemographic variables (age, sex and living situation (alone vs. not alone)) are planned to be included as covariates, too. These variables can be supposed to contribute proportions of variance to the outcome variables which should be independent of possible study effects as the intervention cannot change age, sex or living situation. Thus, the inclusion of these variables should result in decreased residual variance enhancing thereby

the statistical power to detect differences between study groups. A positive intervention effect is then defined as a significant regression coefficient (one-sided test) of the study group variable. The p-values will be interpreted one-sided as one-sided hypotheses are tested. The design of the DelpHi trial allows for multiple testing (five primary outcomes), therefore, additionally the Bonferroni corrected p-values will be reported.

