### **2.3.1.3 Sensitivity Analyses**

Including the GP as random effect variable in the equation using random intercepts only implies that the effect of the GP on the outcome variable is independent of the effects of the predictors which may not be correct for the study group variable and the baseline variable of the outcome. Thus, to test the robustness of the potential treatment effect, in sensitivity analyses random slopes for the baseline variable of the outcome will be introduced into the models. Descriptively, these models allow for GP dependent treatment effect and thus will result in treatment estimates respecting the possibility of differentially collaborating GPs, thus assessing the robustness of the results regardless of a potentially present performance bias.

The treatment effect estimates from the different models will be compared descriptively against each other and, moreover, the random slopes models will be tested against the random intercept models via likelihood ratio tests. Note that these likelihood ratio tests are known to be overly conservative.

Furthermore, in the case of the metric outcomes, we will derive additionally confidence intervals and p-values via non-parametric bootstrapping using 2000 replications. These sensitivity analyses are planned to get confidence intervals and p-values independent on the parametric assumptions of Gaussian distributions and homoscedasticity. Especially in the case of neuropsychiatric symptoms, baseline analyses indicated a skewed distribution for the NPI scores.

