#### **2.4.3 Performance Bias**

As the DelpHi-Trial is conducted in the setting of primary care, the control of the treatment in the control group as “care as usual” is not possible. It could be that already the inclusion of a GP into the study will change the treatment of the included patient. This effect could easily mask potential intervention effects. Thus, a non-significant result cannot be easily interpreted. The treatment adherence of the GPs in the intervention group was evaluated and generally quite high. Nevertheless, it is very plausible that the GPs were different in their adherence to the study protocol. For this reason, we performed special sensitivity analyses (see section “per protocol analyses”). These sensitivity analyses deliver a weak test of the robustness of the effects despite the heterogeneity between the GPs.

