#### **2.5 Post Hoc Power Calculations**

The actual power of the trial was assessed during the baseline sampling when first estimates of the ICCs where known, for reasons explained above. Table 1 gives the estimates for the ICC of the baseline values of the primary efficacy endpoints and the detectable intervention effect (power 80%) given an assumed coefficient of variation of cluster sizes of 1, a baseline follow-up correlation of 0.6,

a mean cluster size of 5 and 100 clusters (GP) included into analysis (total n=500). The power analyses were done with STATA 13/SE using the package *clustersampsi*. Note that the estimates reported in table 1 were derived while the baseline sampling was still ongoing.

**Table 1:** Detectable Difference (power 80%) between Intervention (n=250) and Control group (250)

	Intra-Class Correlation	Detectable Difference	Model
Quality of Life	0.061	0.26	linear
Neuropsychiatric Symptoms	0.361	0.43	linear
Caregiver Burden	0.192	0.35	linear

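### The random-slope likelihood ratio tests are acknowledged to be conservative but left uncorrected, so they detect between-GP variation in the baseline slope somewhat too rarely

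*SAP*

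**What the plan says.** SAP Section 2.3.1.3 (Sensitivity Analyses, per protocol) relaxes the random-intercept assumption of the primary model: "in sensitivity analyses random slopes for the baseline variable of the outcome will be introduced into the models". Two comparisons follow. The first is of estimates: "The treatment effect estimates from the different models will be compared descriptively against each other". The second is formal: "the random slopes models will be tested against the random intercept models via likelihood ratio tests". The paragraph on these models closes with "Note that these likelihood ratio tests are known to be overly conservative".

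The section gives no reference distribution, no significance level and no covariance structure for slope and intercept. It also gives no rule for what follows from a significant or non-significant result.

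Section 2.4.3 (Performance Bias) points back to these analyses as its response to GPs who differ in adherence, and rates them modestly: "These sensitivity analyses deliver a weak test of the robustness of the effects despite the heterogeneity between the GPs". Section 2.3.2.4 drops random slopes from the ITT analyses for computational reasons, so the tests exist only in the per-protocol set.

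**The concern.** The null hypothesis is that the slope variance is zero. A variance cannot be negative, so this value is on the boundary, and the ordinary chi-square distribution is then the wrong reference for the likelihood ratio statistic. Its p-values are too large. The SAP's remark fits only a test read against that ordinary reference, because a test read against the correct mixture would not be conservative. The plan therefore names a miscalibration and leaves it in place.

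The direction matters. In an efficacy test, a p-value that is too large guards against a false claim. In a test meant to reveal that a simpler model is too simple, it makes the departure harder to see. The word conservative may reassure a reader where it should not. At stake is a modest, avoidable loss of sensitivity in the formal comparison of random-slope and random-intercept models.

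**Working it through.** The SAP gives no figure for this test, so there is nothing to reproduce. The check asks how far the uncorrected test departs from its nominal level and what that costs. The 5% level is an assumption throughout.

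**Step 1: true size of the uncorrected test.** Under the null hypothesis the statistic follows a 50:50 mixture of chi-squares.

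- Slope uncorrelated with intercept (one added parameter), mixture of chi-square(0) and chi-square(1), usual cut-off 3.841: 0.5 × P(χ²₁ > 3.841) = 0.5 × 0.05 = 0.025.
- Slope correlated with intercept (two added parameters), mixture of chi-square(1) and chi-square(2), usual cut-off 5.991: 0.5 × P(χ²₁ > 5.991) + 0.5 × P(χ²₂ > 5.991) = 0.5 × 0.0144 + 0.5 × 0.05 = 0.0322.

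**Step 2: cut-offs that restore 5%.** These are 2.71 instead of 3.84 (one parameter) and 5.14 instead of 5.99 (two parameters).

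**Step 3: effect on a printed p-value of 0.08.**

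- One parameter: 0.5 × 0.08 = 0.040.
- Two parameters: the statistic is −2 ln(0.08) = 5.05, and P(χ²₁ > 5.05) = 0.0246, so p = 0.5 × 0.0246 + 0.5 × 0.08 = 0.052.

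**Step 4: simulation under the SAP's planning figures.** Inputs from Section 2.5 are 100 GPs, mean cluster size 5, baseline–follow-up correlation 0.6 and, from Table 1, the quality-of-life ICC of 0.061. The SAP states a coefficient of variation of cluster size of 1; the simulation used about 0.9. Linear mixed models were fitted by maximum likelihood. The outcome was scaled so that the mean slope on baseline is 0.6. The slope standard deviations (SDs) are assumptions, because the SAP gives none.

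With no slope variance (1000 runs), the uncorrected test rejected in 2.3% (uncorrelated) and 3.0% (correlated) of runs, close to Step 1. The corrected test rejected in 4.8% and 4.0%.

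With slope variance (300 runs each), power was:

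| Assumed slope SD | Uncorrelated: uncorrected → corrected | Gain (points) | Correlated: uncorrected → corrected | Gain (points) |
|---|---|---|---|---|
| 0.10 | 7.0% → 15.3% | 8.3 | 8.0% → 11.7% | 3.7 |
| 0.15 | 32.3% → 40.7% | 8.4 | 23.7% → 31.3% | 7.6 |
| 0.20 | 52.0% → 62.7% | 10.7 | 45.3% → 51.3% | 6.0 |
| 0.25 | 84.0% → 88.0% | 4.0 | 76.7% → 81.7% | 5.0 |
| 0.30 | 92.7% → 96.0% | 3.3 | 88.7% → 91.3% | 2.6 |

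The gain runs from 2.6 to 10.7 points. The Monte Carlo standard error of a single power figure is at most √(0.5 × 0.5 / 300) = 2.9 points.

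**The case against.** The strongest reply is that nothing in the SAP is wrong here. The remark is correct, the limitation is disclosed, and the missing reference distribution is silence rather than an error. Part of this stands: the point concerns a better method, not a false statement. But the remark makes sense only for the uncorrected test, and disclosing a miscalibration does not remove it when the remedy is a recalculation of the p-value.

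A second reply is that nothing depends on the test. This stands in full. A reader might infer that the plan will wrongly declare the random-intercept model adequate. No rule says so: a non-significant result neither confirms nor retains any model. Section 2.3.1.2 fixes success without reference to it: "A positive intervention effect is then defined as a significant regression coefficient (one-sided test) of the study group variable". The comparison of treatment estimates does not involve the test's p-value at all.

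A third reply concerns Section 2.4.3. A reader might infer that the conservatism weakens the safeguard against differing GP adherence. The specification does not support that. The slope is on the baseline value, so even a correctly sized test asks whether the baseline-to-follow-up relation varies between GPs, not whether the treatment effect or adherence does. Section 2.3.1.3 does say that these models allow for GP-dependent treatment effects, but the slope it specifies is not on study group, which is constant within a GP because GPs were randomised. That mismatch is a separate and larger matter, and correcting the reference distribution does not cure it. Nor does Section 2.4.3 attribute the weakness it concedes to the likelihood ratio test.

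Finally, correction does not rescue the test where slope variation is small: at a slope SD of 0.10, power is still only 15.3% or 11.7%. Most of the insensitivity there has other causes.

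**Conclusion.** The point holds in a limited form. The planned tests are acknowledged to be conservative and are left so. At a nominal 5% their true size is 2.5% (uncorrelated) or 3.2% (correlated), and they miss between-GP variation in the baseline slope somewhat too often, by about 3 to 11 power points in the scenarios examined.

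The size figures rest on large-sample boundary theory with an intercept variance that is not itself near zero. The simulation supports them at an ICC of 0.061, the smallest in Table 1. The power figures rest on assumed slope SDs and cover linear outcomes only; the two logistic models were not checked.

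The primary efficacy result, the descriptive comparison of treatment estimates and the question of GP adherence are all untouched. The point is minor: a worthwhile correction, not a threat to the trial's conclusions.

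**What to change.** In Section 2.3.1.3, replace the remark on conservatism with a sentence such as:

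> *p-values for the random-slope tests are taken from the 50:50 mixture of chi-square(0) and chi-square(1) if slope and intercept are uncorrelated, or of chi-square(1) and chi-square(2) if correlated; a non-significant result is not evidence that slopes are homogeneous across GPs.*

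These mixtures apply to the planned slope on the baseline value and should not be carried over unexamined to a slope on study group.

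The cost is one sentence. No model is refitted, since each p-value is recalculated from the likelihood ratio statistic already obtained. A parametric bootstrap of the statistic for the logistic models is an optional extra. It does need repeated refitting and is not part of the change asked for.

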### **2.3.1.4 Secondary Analyses**

In secondary analyses, the above described statistical modelling will be performed stratified for the living situation (living alone vs. not living alone). As the intervention targets also the care-giver and

the social context of a person suffering from dementia, it is very plausible that the effects of the intervention are different for persons living alone and persons living not alone. For example, the caregiver burden might response differentially to the intervention. Thus, effect sizes of the intervention for the efficacy endpoints will be derived once for persons living alone and once for persons not living alone. Additionally, to allow an inference-statistical assessment, a study-group living status interaction term will be introduced in the models explained above. A significant interaction term will be interpreted correspondingly that the intervention does not have the same effect for individuals living alone and individuals living not alone.

Moreover, several subgroup analyses regarding differential treatment effects are planned following the workflow of the described stratification living alone vs. not living alone. The subgroups under consideration will be:

- 1) Moderate/severe vs. Mild dementia
- 2) Men vs. Women
- 3) Age under 80 vs Age above 80

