## 2 Analysis Plan

### 2.1 Definition of the Primary Efficacy Endpoints

The design paper defined four dimensions of primary endpoints:

- (1) Quality of life
- (2) Caregiver burden
- (3) Behavioural and psychological symptoms of dementia
- (4) Pharmacotherapy with an antidementia drugs and prevention or suspension of potentially inadequate medication (PIM)

The fourth dimension includes two outcome measurements (antidementia drug treatment) and the suspension of PIM, thus, in total five outcome variables are derived. The first follow-up values on these dimensions (12 months after baseline) were defined as efficacy endpoints.

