### **2.3.2.5 Secondary Analyses (ITT)**

The same analyses will be carried out as described in the per protocol analyses with the difference that missing values in the outcome variable at follow-up will be imputed.

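### A significant interaction is to be read as a difference in effect, and this rule extends to 20 tests per analysis set with no level, correction or exploratory caveat stated

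*SAP*

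**What the plan says.** SAP section 2.1 fixes the number of outcomes: "thus, in total five outcome variables are derived".

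Section 2.3.1.4 plans stratified analyses by living situation and adds a formal test: "a study-group living status interaction term will be introduced in the models explained above". It then says how the test will be read: "A significant interaction term will be interpreted correspondingly that the intervention does not have the same effect". The sentence goes on to name the two living-situation strata, so the rule is written out for that factor only.

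The next paragraph extends the plan: "several subgroup analyses regarding differential treatment effects are planned following the workflow of the described stratification living alone vs. not living alone". It lists three factors: dementia severity, sex and age.

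Section 2.3.2.5 repeats the programme on imputed data: "The same analyses will be carried out as described in the per protocol analyses".

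The only multiplicity correction in the SAP is in section 2.3.1.2: "The design of the DelpHi trial allows for multiple testing (five primary outcomes), therefore, additionally the Bonferroni corrected p-values will be reported". The same section gives the only statement on sidedness, for the study-group coefficient: "The p-values will be interpreted one-sided as one-sided hypotheses are tested". Section 2.3.1.4 says nothing on either matter for the interaction terms.

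**The concern.** The rule in section 2.3.1.4 is inferential. A term that reaches significance becomes a conclusion that the intervention acts differently in two groups. With many such tests and no correction, a significant term or two is expected by chance even if the effect is the same everywhere, and the rule has no means of telling such a result from a real difference.

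The SAP recognises this problem elsewhere. In section 2.2 it reduces the 20 BIZA-D scales to one principal component, because testing the scales one by one would multiply the tests too far. Section 2.3.1.4 plans the same number of tests without a safeguard.

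At stake is what the trial may say about subgroups. The primary conclusions do not depend on these tests.

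**Working it through.** The SAP states no error rate or test count for the interactions, so there is no figure of its own to reproduce.

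**Inputs**
- Outcomes: 5 (section 2.1).
- Factors: living situation plus severity, sex and age = 4 (section 2.3.1.4). The last three come in through the reference to the same workflow.
- Level per test: not given. 5% is assumed; 2.5% and 1% are shown as the range.

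**Number of tests.** 4 × 5 = 20 per analysis set, of which 5 concern living situation and 15 the other factors.

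**Expected false positives with no true interaction.** 20 × 0.05 = 1 per set. This holds whatever the correlation between the tests.

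**Chance of at least one false positive, independent tests:** 1 − (1 − a)^k.

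| Tests (k) | Level (a) | Result |
|---|---|---|
| 20 | 0.05 | 1 − 0.95^20 = 64.2% |
| 20 | 0.025 | 1 − 0.975^20 = 39.7% |
| 20 | 0.01 | 1 − 0.99^20 = 18.2% |
| 15 (without living situation) | 0.05 | 1 − 0.95^15 = 53.7% |
| 5 (living situation only) | 0.05 | 1 − 0.95^5 = 22.6% |

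For 20 independent tests the chance passes 50% at a level of 1 − 0.5^(1/20) = 0.034 per test.

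**Correlation.** The outcomes are measured in the same patients, so independence is too simple. Sets of two-sided z-tests with no true interaction were simulated at 5% per test (200,000 to 300,000 draws). All correlations are assumptions.
- Moderate mix: quality of life, NPI and caregiver burden correlated 0.4 to 0.6 in absolute value, other outcome pairs 0.1, factors 0 to 0.3. Result: 58.5% to 60.9% for 20 tests, and 49.1% to 50.9% for the 15 tests without living situation.
- All outcomes correlated 0.5, factors independent: 55.4%.
- Strong correlation: 48.6% with outcomes and factors both at 0.5, and 47.4% with all outcomes at 0.7 and independent factors.

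**If a correction applied.** Bonferroni over the five outcomes within each factor (0.05/5 = 0.01 per test) would leave 18.2% across the four factors. Bonferroni over all 20 (0.05/20 = 0.0025) would give 1 − 0.9975^20 = 4.9%.

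**The case against.** Several points on the other side have weight.

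- **Scope of the rule.** It is written for living situation alone, where five tests give 23%. That it covers the other three factors is an inference from the wording on workflow. The inference is reasonable, since the interaction test is part of that workflow, but it is an inference.
- **A real living-situation effect.** The SAP calls such a difference very plausible and gives a reason: the intervention also addresses the caregiver and social context. If those interactions are real, a significant one is not a false finding, and only the other 15 tests are at issue. For them the chance at 5% is about one half. The SAP gives no comparable rationale for severity, sex or age.
- **Carry-over of the correction.** The interaction terms enter the models of section 2.3.1.2, so the five-outcome Bonferroni might be taken to come with them. The text does not say so. Even there, corrected p-values are reported in addition and are not named as the basis for decisions.
- **Status of the analyses.** Section 1 calls the trial exploratory, and these are secondary analyses with few, pre-named factors and a proper interaction test. This limits the weight of the point. However, section 1 ties the word to the lack of known effect sizes, and nothing in section 2.3.1.4 softens the reading rule.

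A reader might infer two stronger statements. The first is that a false subgroup claim is more likely than not, without conditions. The SAP does not support that: the figure needs a level it does not give, no true interaction, and no strong correlation. The second is an 87% chance over both analysis sets (1 − 0.95^40). That treats the ITT repeat as independent of the complete-case analysis, although both use largely the same patients, so the figure is not usable. Nor does the SAP say that subgroup results would decide who is offered the intervention.

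**Conclusion.** The point holds as a defect in the reading rule. The SAP turns a significant interaction into a conclusion that effects differ, extends that approach to 20 tests per set, names no set as the one that counts, and states no level, sidedness, correction or caveat for them. At an assumed 5% per test and with no true interaction, one false positive is expected per set. The chance of at least one is 64% under independence, about 58–61% under moderate assumed correlation, and below 50% only if correlation is strong. At 2.5% per test it is 40% under independence. Every one of these figures is well above 5%, but none can be quoted without its conditions. Because the analyses are secondary, the matter concerns the subgroup statements only.

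**What to change.** In section 2.3.1.4, replace the sentence that interprets a significant interaction. The new text should say, for all four factors, that:
- each interaction is reported as an estimate with a 95% confidence interval, whether significant or not;
- the number of tests (20) is stated beside the results;
- the tests are two-sided, as no direction is set for the interactions;
- the results generate hypotheses and do not by themselves show that the effect differs.

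Name one analysis set for these results and present the other as supportive, with a matching line in section 2.3.2.5. Section 1 dates the follow-up analyses to April to October 2016, so if the set is chosen now, the report should say that it was chosen afterwards.

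A multiplicity-adjusted p-value, for example Holm over the 20 tests, may be shown alongside. It need not be a condition for discussing an interaction: for secondary tests in a trial described as exploratory, the loss of power makes such a gate debatable.

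The cost is a few sentences and, if wanted, one table column; no new data are needed. The drawback is a weaker subgroup statement, including for living situation, where the SAP has a reason to expect a difference.
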